6.11.3 Descriptive summaries and listing

MELD score observed values, absolute change from baseline and percentage change from baseline will be summarised and listed by treatment group and visit.

6.12 Secondary Endpoints

6.12.1 Change in total bilirubin from baseline to Day 7, 14, 21 and 28

Total bilirubin concentration is a marker of hepatic function.

6.12.1.1 Analysis

Change in total bilirubin from baseline up to and including day 28 will be assessed with an MMRM analysis, using the FAS, including terms for treatment group, visit, treatment-by-visit interaction as fixed effects and the baseline total bilirubin value as a covariate. The adjusted treatment means and adjusted mean difference between the active dose and placebo will be presented along with 95% CI and p-value at days 7, 14, 21 and 28.

The modelling process described in section [6.11.1](#) will be followed.

6.12.1.2 Descriptive summaries and listing

Covered under section [16.7](#).

6.12.2 Proportion of patients showing a 25% reduction of bilirubin at Day 7, 14, 21 and 28

The proportion of patients showing a 25% reduction of total bilirubin at days 7, 14, 21 and 28 will be compared between treatment groups using a MMRM logistic regression model.

At each visit, patients with $\geq 25\%$ reduction in total bilirubin from baseline will be assigned a value of 1 (indicating 25% reduction achieved) while patients with a $< 25\%$ reduction will be assigned a value of 0 (indicating 25% reduction not achieved).

The model will include treatment, visit, treatment-by-visit as fixed effects and baseline bilirubin as a covariate.

The variance/covariance matrix structure that results in best model fit will be selected using the process described in section [6.11.1](#). The adjusted LS estimate for the treatment odds of achieving the endpoint and treatment odds ratio (DS102:Placebo) and corresponding 95% CIs and p-value corresponding to the treatment odds ratio will be presented.

6.12.2.1 Descriptive summaries and listing

The number and percentage of patients showing and patients not showing a 25% reduction of bilirubin at days 7, 14, 21 and 28 will be presented by treatment group.

6.12.3 Change in serum Cytokeratin-18 M30/M65 from baseline to Day 7, 14, 21 and 28

Change in serum cytokeratin18-M30/M65 from baseline up to and including day 28 will be assessed with an MMRM analysis, using the FAS, including terms for treatment group, visit and treatment-by-visit interaction as fixed effects and the baseline serum cytokeratin18-M30/M65 value as a covariate. The adjusted treatment means and adjusted mean difference between the active dose and placebo will be presented along with 95% CIs and p-value at days 7, 14, 21 and 28.

The modelling process described in section 6.11.1 will be followed.

6.12.3.1 Descriptive summaries and listing

Serum cytokeratin18-M30/M65 observed values, absolute change from baseline and percentage change from baseline will be listed and summarised by treatment group and visit.

6.12.4 Change in AST levels from baseline to Day 7, 14, 21 and 28

Aspartate aminotransferase is liver enzyme and a marker of liver injury.

6.12.4.1 Analysis

Change in AST from baseline up to and including day 28 will be assessed with an MMRM analysis, using the FAS, including terms for treatment group, visit and treatment-by-visit interaction as fixed effects and the baseline AST value as a covariate. The adjusted treatment means and adjusted mean difference between the active dose and placebo will be presented along with 95% CI and p-value at days 7, 14, 21 and 28.

The modelling process described in section 6.11.1 will be followed.

6.12.4.2 Descriptive summaries and listing

Covered under section [16.7](#).

6.12.5 Change in AST:ALT ratio from baseline to Day 7, 14, 21 and 28

Change in AST:ALT from baseline up to and including day 28 will be assessed with an MMRM analysis, using the FAS, including terms for treatment group, visit and treatment-by-visit interaction as fixed effects and the baseline AST:ALT value as a covariate. The adjusted treatment means and adjusted mean difference between the active dose and placebo will be presented along with 95% CI and p-value at days 7, 14, 21 and 28.

The modelling process described in section 6.11.1 will be followed.

6.12.5.1 Descriptive summaries and listing

Covered under section [16.7](#).

6.12.6 Change in MDF score from baseline to Day 7, 14, 21 and 28

The Maddrey discriminant function (MDF) is a measure of liver dysfunction and a method of assessing disease severity.

6.12.6.1 Analysis

Change in MDF score from baseline up to and including day 28 will be assessed with an MMRM analysis, using the FAS, including terms for treatment group, visit and

treatment-by-visit interaction as fixed effects and the baseline MDF value as a covariate. The adjusted treatment means and adjusted mean difference between the active dose and placebo will be presented along with 95% CI and p-value at days 7, 14, 21 and 28.

The modelling process described in section 6.11.1 will be followed.

6.12.6.2 Descriptive summaries and listing

MDF score observed values, absolute change from baseline and percentage change from baseline will be listed and summarised by treatment group and visit.

6.12.7 Proportion of patients showing a 25% reduction in MELD score from baseline to Day 7, 14, 21 and 28

The proportion of patients showing at least a 25% reduction in MELD score at days 7, 14, 21 and 28 will be compared between treatment groups using a MMRM logistic regression model.

At each visit, patients with $\geq 25\%$ reduction from baseline will be assigned a value of 1 (indicating 25% reduction achieved) while patients with a $< 25\%$ reduction will be assigned a value of 0 (indicating 25% reduction not achieved).

The model will include treatment, visit, treatment-by-visit interaction as fixed effects and baseline MELD score as a covariate.

The variance/covariance matrix structure that results in best model fit will be selected using the process described in section [6.11.1](#).

The adjusted LS estimate for the treatment odds of achieving the endpoint and treatment odds ratio (DS102:Placebo) along with corresponding 95% CIs and p-value (corresponding to the treatment odds ratio) will be presented at days 7, 14, 21 and 28.

6.12.7.1 Descriptive summaries and listing

The number and percentage of patients showing and patients not showing a 25% reduction in MELD score at days 7, 14, 21 and 28 will be presented by treatment group.

6.12.8 Change in MELD score from baseline to Day 7, 14 and 21

Estimates for the adjusted treatment LS means and adjusted mean LS difference between the active dose and placebo will be presented along with 95% confidence intervals (CI) and p-value for days 7, 14 and 21 will be obtained from the model fitted in section [6.11.1](#) and presented in the same table as the primary endpoint.

6.12.8.1 Descriptive summaries and listing

Covered under section [6.11.3](#).

6.12.9 Change in m-SOFA total score from baseline to Day 7, 14, 21 and 28

The m-SOFA score is used in the assessment of disease severity, as well as in predicting mortality.

A score between 0 - 4 will be assigned to the following organ systems parameters: Respiratory, liver, cardiovascular, central nervous system (CNS) and renal. Respiratory function will be measured by SpO₂/FiO₂, liver function will be classified as scleral icterus or jaundice or no scleral icterus or jaundice, cardiovascular function will check for hypotension, CNS function will be measured using the Glasgow coma score and renal function will be measured by creatinine (mg/dL) levels. A total score

m-SOFA score is derived from the individual scores. For this study, the m-SOFA score is recorded in the eCRF.

6.12.9.1 Analysis

Change in m-SOFA score from baseline up to and including day 28 will be assessed with an MMRM analysis, using the FAS, including terms for treatment group, visit, treatment-by-visit interaction as fixed effects and the baseline m-SOFA value as a covariate. The adjusted treatment means and adjusted mean difference between the active dose and placebo will be presented along with 95% CI and p-value at days 7, 14, 21 and 28.

The modelling process described in section 6.11.1 will be followed.

6.12.9.2 Descriptive summaries and listing

m-SOFA score observed values, absolute change from baseline and percentage change from baseline will be listed and summarised by treatment group and visit.

6.12.10 Proportion of patients with a 2-point worsening of m-SOFA from baseline to Day 7, 14, 21 and 28

6.12.10.1 Analysis

The proportion of patients showing a 2-point worsening/increase in m-SOFA score at days 7, 14, 21 and 28 will be compared between treatment groups using a MMRM logistic regression model.

At each visit, patients achieving a ≥ 2 -point increase in m-SOFA score from baseline will be assigned a value of 1 (indicating a 2-point worsening) while patients achieving < 2 -point increase in MELD score will be assigned a value of 0 (indicating not a 2-point worsening).

The model will include treatment, visit, treatment-by-visit interaction and baseline m-SOFA score as a covariate.

The variance/covariance matrix structure that results in best model fit will be selected using the process described in section [6.11.1](#).

The adjusted LS Means for the treatment odds of achieving the endpoint and treatment odds ratio (DS102:Placebo) along with corresponding 95% CIs and p-value (corresponding to the treatment odds ratio) will be presented at days 7, 14, 21 and 28.

6.12.10.2 Descriptive summaries and listing

The number and percentage of patients showing and patients not showing a two-point worsening in m-SOFA at days 7, 14, 21 and 28 will be presented by treatment group.

6.12.11 Change in hepatic encephalopathy as assessed by West Haven Criteria, from baseline to Day 7, 14, 21 and 28

The West Haven Criteria is used to classify the severity of hepatic encephalopathy with a grading of 1 – 4, grade 1 being the least serious with the patient having a trivial lack of awareness to grade 4 in which the patient is in a state of unconsciousness.

6.12.11.1 Analysis

West Haven Criteria data will be analysed using an MMRM ordinal logistic regression model. The model will include treatment, visit and treatment-by-visit interaction as fixed effects and baseline west haven criteria as a covariate.

The variance/covariance matrix structure that results in best model fit will be selected using the process described in section [6.11.1](#).

Assumptions about the proportionality of odds will also be assessed. Should assumptions not hold an alternative approach to the analysis will be decided following the BDRM and will be detailed in a SAP amendment.

The LS estimate for the treatment odds of achieving the endpoint and treatment odds ratio (DS102:Placebo) along with corresponding 95% CIs and p-value (corresponding to the treatment odds ratio) will be presented at days 7, 14, 21 and 28.

6.12.11.2 Descriptive summaries and listing

West Haven Criteria observed values and absolute change from baseline will be listed and summarised by treatment group and visit.

6.12.12 Incidence of acute kidney injury over 28 days

The number and percentage of patients who experienced an acute kidney injury between baseline and day 28 will be summarised by treatment group. The associated 95% Clopper-Pearson exact confidence intervals will also be presented.

Details of treatment measures undertaken for the acute kidney injury will also be summarised.

All acute kidney injury data will be listed.

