### 5.2 Secondary Endpoints

- Change in total bilirubin from baseline to Day 7, 14, 21 and 28
- Proportion of patients showing a 25% reduction of bilirubin at day 7, 14, 21, and 28.
- Change in serum Cytokeratin18-M30/M65 from baseline to Day 7, 14, 21 and 28
- Change in AST levels from Baseline to Day 7, 14, 21 and 28
- Change in AST:ALT ratio from Baseline to Day 7, 14, 21, 28
- Change in MDF score from baseline to Day 7, 14, 21 and 28.
- Proportion of patients showing a 25% reduction in MELD score from baseline to Day 7, 14 and 21
- Change in m-SOFA from baseline to Day 7, 14, 21 and 28
- Proportion of patients with a 2-point worsening of m-SOFA from baseline at Day 7, 14, 21 and 28
- Change in hepatic encephalopathy as assessed by West Haven criteria, from baseline at Day 7, 14, 21 and 28 from baseline to Day 28
- Incidence of acute kidney injury over 28 days (defined by requiring medicinal or mechanical support)
- Incidence of variceal haemorrhage, ascites or hepatic encephalopathy over 28 days

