### **12.8.3 Secondary variables**

The secondary and exploratory efficacy variables will be summarised with descriptive statistics per treatment group and visit. The change from baseline to Day 28 (and other visits) for the active treatment group will be compared against placebo either via logistic regression or analysis of covariance taking the baseline level as covariate into account. Survival time will be analysed using the Cox Proportional Hazards model including treatment group and MELD score at baseline as covariate. The 5% level of significance will be used for all treatment comparisons of secondary and exploratory endpoints without adjustment for multiplicity.

A new secondary efficacy variable will be a 5-level ordinal variable combining change of MELD score from baseline, premature treatment terminations and mortality as follows; each patient will be allocated to the first level that occurs

- level 1: death within 28 days,
- level 2: death within 90 days,
- level 3: early treatment termination because of safety issues or lack of efficacy,
- level 4: no improvement in Meld Score at day 28 compared to baseline,
- level 5: improvement in Meld Score at day 28 compared to baseline

Patients with lost to follow up within 28 days will be allocated to level 4 or 5 according to their imputed result at day 28 based on the model in 12.9.2 as for these patients the MAR assumption seems appropriate.

This ordinal variable will be analysed using ordinal logistic regression with MELD score as baseline covariate ( $\alpha=0.05$  two-sided). An odds ratio including 95%-confidence limits will be calculated as measure of effect size for this variable.

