6 ANALYSIS PLAN

6.1 General

The decision to proceed to the double-blind phase of this study will be determined by the DSMB following review of the safety and pharmacokinetic data from the pilot phase as detailed in the DSMB charter. No statistical outputs will be produced for the DSMB review as part of this SAP, details of the PK analysis for the pilot study are included in Appendix 1. Patients from the pilot phase will be included in the same listings for the double-blind phase as a separate group. Should the study be discontinued after the pilot phase, the listings described in the sections below will be produced for the pilot phase only.

The summary tables and figures described in the following sections relate to the main, double-blind, study only unless specifically mentioned otherwise.

Summary statistics for continuous variables will consist of number of non-missing observations (n), mean, standard deviation (SD), minimum, 25th percentile (Q1), median, 75th percentile (Q3), and maximum, unless specified otherwise. The precision of these variables is defined in the table, figure and listing shells document.

For categorical variables the number and percentage of patients in each category will be presented, based on the number of non-missing observations apart from disposition of patients, protocol deviations, background and demographic characteristics, prior and concomitant medications/procedures and adverse events where the percentage will be based on the number of patients in the analysis set.

All statistical tests will be performed using a two-tailed 5% overall significance level, unless otherwise stated. The null hypothesis at all times will be that the treatments are equivalent. All comparisons between the treatments will be reported with 95% confidence intervals for the difference.

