6.12.13 Incidence of variceal haemorrhage, ascites or hepatic encephalopathy over 28 days

The number and percentage of patients who experience a variceal haemorrhage between Baseline and Day 28 will be summarised by treatment group. The associated 95% Clopper-Pearson exact confidence intervals will also be presented.

The number and percentage of patients who have ascites between baseline and day 28 will be summarised by treatment group. The associated 95% Clopper-Pearson exact confidence intervals will also be presented.

Patients who have a hepatic encephalopathy score of 2 or 3 in the data collected for the Child-Pugh score will be classed as having hepatic encephalopathy (Yes). Any patient with a score of 1 will be classed as not having hepatic encephalopathy (No). the number and percentages of patients who have hepatic encephalopathy between baseline and day 28 will be summarised by treatment group. The associated 95% Clopper-Pearson exact confidence intervals will also be presented.

All variceal haemorrhage and ascites data will be listed. Hepatic encephalopathy will be included into the Child-Pugh listing.

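### The 28-day incidences of acute kidney injury, variceal haemorrhage, ascites and encephalopathy are the only secondary endpoints for which the SAP plans no DS102-versus-placebo contrast

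*SAP*

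**What the plan says.** Protocol 5.2 and SAP 2.2 both list two incidence endpoints among the secondary endpoints. One is acute kidney injury over 28 days, defined by the need for medicinal or mechanical support. The other is "Incidence of variceal haemorrhage, ascites or hepatic encephalopathy over 28 days".

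SAP 6.12.12 handles the first as follows: "The number and percentage of patients who experienced an acute kidney injury between baseline and day 28 will be summarised by treatment group". SAP 6.12.13 splits the second into three components and treats each alike, for example: "The number and percentage of patients who experience a variceal haemorrhage between Baseline and Day 28 will be summarised by treatment group". Each of the four incidences also receives a 95% Clopper-Pearson interval. Encephalopathy is counted here from the Child-Pugh item (score 2 or 3), not from West Haven grade. Neither section names a between-arm estimate or test.

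For secondary and exploratory variables, Protocol 12.8.3 first plans descriptive summaries and then says: "The change from baseline to Day 28 (and other visits) for the active treatment group will be compared against placebo either via logistic regression", with ANCOVA as the alternative. It adds: "The 5% level of significance will be used for all treatment comparisons of secondary and exploratory endpoints without adjustment for multiplicity". SAP 6.14 treats all secondary endpoints as descriptive evidence without multiplicity adjustment.

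**The concern.** The efficacy objective in both documents is to compare DS102 with placebo. A Clopper-Pearson interval describes one proportion, so two of them side by side estimate no treatment effect. Whether they overlap is also an unreliable guide to whether the arms differ.

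The omission looks unintended. The SAP models a contrast, with a confidence interval and p-value, for every secondary endpoint in 6.12.1 to 6.12.11, and for the exploratory laboratory values and scores as well. SAP 6.25 records departures as small as an added Day 21 time point but is silent on this one.

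At stake is the estimation and reporting of four clinical-event outcomes. If no effect measure is fixed in advance, anyone who wants one will choose the scale and method after unblinding.

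**Working it through.** **1. Which endpoints are compared, and where**

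| Endpoint | SAP section | Planned contrast |
|---|---|---|
| Secondary endpoints in 6.12.1 to 6.12.10 | 6.12.1 to 6.12.10 | Adjusted mean difference or odds ratio, CI, p-value |
| Encephalopathy, West Haven grade by visit | 6.12.11 | Odds ratio, CI, p-value |
| Acute kidney injury, 28-day incidence | 6.12.12 | None |
| Variceal haemorrhage, ascites, encephalopathy (Child-Pugh item), 28-day incidence | 6.12.13 | None |
| Death | 6.13.1 | Cox hazard ratio, CI, p-value |
| Five-level outcome (death, early termination, MELD) | 6.13.7 | Odds ratio, CI, p-value |

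Kidney injury, variceal haemorrhage and ascites as events therefore have no contrast anywhere. Ascites otherwise appears only as one item within the Child-Pugh score. For encephalopathy, only the incidence form lacks a contrast.

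**2. Sample size available**

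The plan's own figure concerns the primary endpoint. For d = 0.54 and 55 per group, the noncentrality is 0.54 × √(55/2) = 2.83 on 108 degrees of freedom. The two-sided 5% t-test then has power 0.8014, which matches Protocol 12.3; 54 per group gives 0.794. With all 60 randomised per group, power is 0.835. Neither document states a sample size, power or event rate for the four incidences, so every event count and rate below is an assumption.

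**3. Can per-arm intervals stand in for a comparison?**

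Assume 10/60 events on DS102 and 21/60 on placebo.
- Clopper-Pearson, as planned: 8.3% to 28.5% and 23.1% to 48.4%. They overlap.
- Risk difference, DS102 minus placebo: 16.7% − 35.0% = −18.3 points.
- Newcombe interval: d − √[(p₁−l₁)² + (u₂−p₂)²] to d + √[(u₁−p₁)² + (p₂−l₂)²], where l and u are the Wilson limits, here 9.3% to 28.0% and 24.2% to 47.6%. 
 - Lower limit: −18.3 − √(7.35² + 12.64²) = −33.0. 
 - Upper limit: −18.3 + √(11.36² + 10.83²) = −2.6.
- Fisher exact p = 0.036.

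The same happens at 8/60 versus 18/60: intervals of 5.9% to 24.6% and 18.8% to 43.2% overlap, while the difference is −16.7 points (−30.7 to −1.9), Fisher p = 0.045.

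These examples are borderline. 10 versus 20 gives Fisher p = 0.057, and at 10 versus 19 the Newcombe interval includes zero (−29.6 to 0.4). They show that overlap can mislead, not that it usually will.

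**4. How precise would the contrast be?**

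Take 60 per arm, two-sided 5%, and a halving of the placebo rate. Power = Φ[(|p₁−p₂| − 1.96·SE₀)/SE₁], with SE₀ pooled and SE₁ unpooled. At 30% versus 15%, SE₀ = √(0.225 × 0.775 × 2/60) = 0.0762 and SE₁ = √((0.21 + 0.1275)/60) = 0.0750. Power is Φ[(0.15 − 0.1494)/0.0750] = 50%.

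| Assumed placebo rate | Power for a halving | n per arm for 80% | Example counts, DS102 vs placebo | Risk difference, points (95% CI) |
|---|---|---|---|---|
| 10% | 18% | 435 | 3 vs 6 | −5.0 (−15.7 to 5.2) |
| 20% | 33% | 199 | 6 vs 12 | −10.0 (−22.9 to 3.0) |
| 30% | 50% | 121 | 8 vs 18 | −16.7 (−30.7 to −1.9) |
| 50% | 82% | 58 | 18 vs 30 | −20.0 (−35.9 to −2.5) |

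The counts in the last two rows are illustrations and not exact halvings.

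**The case against.** A reader might infer that the trial yields no treatment effect on its important clinical events. The documents do not support that. Death has a hazard ratio, West Haven grade has an odds ratio at four visits, and the five-level outcome has an odds ratio. Two-point worsening of m-SOFA, which has a creatinine component, also has an odds ratio. None of these is the 28-day incidence of kidney injury, variceal haemorrhage or ascites, so a narrower gap remains.

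A reader might also infer that the protocol expressly promises these comparisons and that the SAP breaks the promise. The sentence in Protocol 12.8.3 has change from baseline as its subject and does not name the incidence endpoints. Its logistic regression has other natural targets in the bilirubin, MELD and m-SOFA responder endpoints. A planned comparison is therefore a reasonable reading, supported by the adjacent sentence on all secondary comparisons, but an undeclared departure is not established. SAP 6.1 does not settle it: "All comparisons between the treatments will be reported with 95% confidence intervals for the difference" governs comparisons that are made and does not require one for every endpoint.

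The trial is exploratory, secondary endpoints are descriptive, counts per arm will be published, and nothing in the plan tells anyone to judge by overlap. All true, and these points limit the harm. But descriptive status has not stopped the SAP from estimating an effect for every other secondary endpoint.

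The strongest practical objection is that a crude difference would not be clean. SAP 6.12.13 counts patients who have ascites or encephalopathy between baseline and Day 28. Protocol 7.3 excludes only refractory ascites and grade 4 encephalopathy, and Protocol 13.2 foresees patients entering with grade II or III. Existing and new cases would be mixed. Death before Day 28 also removes patients from observation. The baseline point stands and shapes the fix; the deaths limit interpretation.

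**Conclusion.** The point holds in a limited form. Four 28-day incidences are the only secondary endpoints without a DS102-placebo contrast. For three of them as events (kidney injury, variceal haemorrhage, ascites) no contrast exists anywhere in the SAP; for encephalopathy only the incidence form lacks one. The plan is out of step with its efficacy objective and with its own treatment of the other secondary endpoints, and SAP 6.25 is silent.

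The consequence is for estimation and reporting; the primary inference is unaffected. The contrast would often be inconclusive: power for a halving is about 18%, 33%, 50% and 82% at assumed placebo rates of 10%, 20%, 30% and 50%. That is a reason to show the width of the interval, not to leave it out. These figures rest on assumed rates and on all 60 patients per arm being counted. The correction is worth making because it is nearly free.

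**What to change.** Before unblinding, amend SAP 6.12.12 and 6.12.13:

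- For each of the four incidences, report the DS102 minus placebo risk difference with a Newcombe or Miettinen-Nurminen 95% CI.
- Optionally add an odds ratio from logistic regression, using Firth or exact methods if events are sparse.
- For ascites and encephalopathy, adjust for the condition at baseline, or report patients with and without it at baseline separately.
- Label these results descriptive, as in SAP 6.14.

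If the sponsor prefers per-arm summaries only, SAP 6.25 should say so and give the reason.

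The cost is a few lines of SAP text and one extra table column, plus a baseline split for two events. No new data collection is needed: ascites data and the Child-Pugh score are already scheduled at baseline. The price in interpretation is wide intervals, which should be stated with the results.
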